4. Special Populations

Does this project involve any of the following:

Research on Children? no

Research with Prisoners? no

If yes, complete the Prisoners in Research Form and upload to IRBNet as supporting documentation

Research with Pregnant Women? no

Research with any other vulnerable population (e.g. cognitively impaired, economically disadvantaged, etc.)? please describe no

5. RESEARCH ABSTRACT

Please provide a brief description in LAY language (understandable to an 8th grade student) of the aims of this project.

Up to 48% of adults following a lower-limb amputation will die within the upcoming year.¹ Lack of physical activity (exercise) contributes to high death rates.^{2,3} It is recommended that younger (and middle-aged) adults without a health condition walk 10,000 steps/day to reduce the risk of chronic health conditions, while recommendations are 7,100 steps per day for older adults and those with chronic health conditions.⁴ Adults with a lower-limb amputation walking about 21-43%⁵⁻⁷ of the recommended 7,100 steps/day.⁴ Step activity monitors, such as the StepWatch (a research-grade accelerometer) and the FitBit (a commercially-available monitor) provide a means of evaluating physical activity, which is important since patients tend to over-estimate their level of physical activity.^{8,9} Activity monitor use, however, may not be possible in every healthcare practice setting, as monitors may cost \$100-\$600 and someone must remove the data from the monitor, interpret the

data, and enter the data into the patient's medical record. Therefore, physical activity questionnaires, where the patient self-reports their physical activity, are ideal in a clinical setting. Unfortunately, to date, there has been little research looking at the accuracy of physical activity questionnaires in patients with lower-limb amputations and how these questionnaires measure up to data obtained from step activity monitors.

In addition to 7,100 steps/day, adults with mobility-limiting, chronic conditions (including individuals with lower-limb amputations) should participate in ≥ 150 minutes of moderate-intensity physical activity per week, with activity in ≥ 10 minutes per bout.⁴ Moderate-intensity activity has been defined as 3 metabolic equivalents (METs).¹⁰ One MET is equal to the amount of oxygen one consumes at rest, so 3 METs means that one is consuming 3 times the amount of oxygen one would consume at rest. In healthy adults without a medical condition this equates to walking 2.6-2.7 mph¹¹ or 100 steps/minute¹², while for adults with an amputation of the leg below-the-knee (i.e. a transtibial amputation), 1.47 mph or 86 steps/minute has been reported to equal 3 METs.¹⁰ Maximal walking speeds for adults with lower-limb amputations, specifically those who have lost their limb due to poor blood circulation may be ≤ 1.67 mph,¹³⁻¹⁵ so one must question if walking 1.47 mph for an extended time is possible for these patients. We believe that 1.47 mph is greater than 3 METs for adults with a lower-limb amputation who have other medical issues, such as diabetes and peripheral vascular disease, and who are deconditioned and not participating in physical activity.

It is important to know what speed (mph) and cadence (steps/minute) equals 3 METs in adults with a lower-limb amputation with other medical conditions who are currently inactive. We believe that these patients represent the vast majority of patients that healthcare providers encounter and must council regarding increasing their physical activity. Providers need to know what speed and cadence is equal to 3 METs for inactive patients with limb loss with other medical conditions, so that providers can appropriately advise their patients and prescribe exercise.

Walking exercise may occur over-ground or on a treadmill. When an individual with a lower-limb amputation is walking over-ground, their right-to-left side walking pattern will be more asymmetrical (uneven) when compared to when they are walking on a treadmill.¹⁶ When walking is more symmetrical side-to-side (even), the patient may have to expend more energy. Energy expenditure can be assessed as the amount of oxygen consumed, which can be obtained while wearing a mask that evaluates your breathing while walking. Among adults with a lower-limb amputation, energy expenditure studies have generally used treadmills to look at energy expenditure.¹⁷⁻²⁰ Over-ground versus treadmill conditions, however, are different,²¹ and as such, what equals 3 METs (speed, cadence) in each walking condition may vary.²²

Further, no studies have compared the energy cost of walking in adults who are inactive with a lower-limb amputation to age-, sex-, and body mass index (computed from height and weight) - matched adults without an amputation. While studies have evaluated the impact of aging^{52,53} and limb length of the amputated limb^{49,51} on energy expenditure, few have evaluated modifiable factors that may impact energy expenditure among adults with lower-limb amputation.^{56,57} Similarly, little research has explored modifiable factors that may impact physical activity levels.^{54,55}

The project's goal is to provide knowledge that will improve physical activity prescription for inactive adults with a single, below-the-knee amputation (i.e. transtibial amputation).

Successful completion of the project may provide healthcare providers with (1) a physical activity self-report measure that can be used in clinical practice for patients with a lower-limb amputation, (2) gait speed (mph) for prescribing moderate-intensity over-ground and treadmill walking during the rehabilitation of patients with lower-limb amputations, and (3) cadence (steps/minute), for evaluating and monitoring moderate-intensity physical activity via step activity monitors, for inactive adults with a lower-limb amputation.

We will provide the first objective data that looks at the additional energy expenditure necessary for inactive adults with a lower-limb amputation who are using a prosthesis to walk short-distances as compared to able-bodied adults; this data may be used for the development of future prosthetic components that reduce energy expenditure. We will explore factors that may be linked to energy expenditure and physical activity among adults with and without a lower-limb amputation.

Specific Aim 1: Evaluate reliability and validity of physical activity self-report measures (i.e. International Physical Activity Questionnaire, Incidental and Planned Exercise Questionnaire-past week^{23,24}) as compared to physical activity characteristics obtained via step activity monitors (i.e. time spent walking/day, walking bout duration, walking bouts/day) among inactive adults with a single-limb amputation (n=20).

Hypothesis: *H1a: Both self-report measures will have excellent test-retest reliability (ICCs $\geq .75$). H1b: At least 1 self-report measure will demonstrate validity with ≥ 2 physical activity characteristics.*

Specific Aim 2: Determine what gait speed (mph) and cadence (steps/minute) constitute 3 METs, i.e. moderate-intensity activity, among inactive adults with a single, below-the-knee amputation during over-ground and treadmill walking (n=20).

Hypothesis: *H2a: 3 METs will occur at slower speeds during treadmill walking as compared to over-ground walking. H2b: 3 METs will occur at slower cadences during treadmill walking as compared to over-ground walking.*

Specific Aim 3: Evaluate differences in energy expenditure based on oxygen consumption between inactive adults with a single, below-the-knee amputation (n=20) and matched controls (n=20) during short bouts of over-ground and treadmill walking at self-selected gait speeds, 75% and 125% of self-selected gait speeds.

Hypothesis: *H3: Energy expenditure will be significantly greater at all walking speeds for adults with a limb amputation as compared to controls (a) over-ground and (b) during treadmill walking ($p \leq 0.05$).*

Specific Aim 4: Explore modifiable factors that may impact energy expenditure (assessed via oxygen consumption) including comorbidities, fatigue, sleep disturbance, balance, functional lower extremity strength, functional mobility, and agility among adults with (n=20) and without a unilateral below-the-knee amputation (n=20).

Hypotheses: For both adults with and without a below-the-knee amputation (after controlling for covariates):

H4a: Comorbidities: Energy expenditure will be significantly greater at all walking speeds and for both walking conditions (over-ground and treadmill) for adults with greater comorbidity burden as assessed with the Cumulative Illness Rating Scale.

H4b: Fatigue: Energy expenditure will be significantly greater at all walking speeds and for both walking conditions (over-ground and treadmill) for adults who indicate fatigue on the PROMIS-29, as compared to those who do not indicate fatigue.

H4c: Sleep Disturbance: Energy expenditure will be significantly greater at all walking speeds and for both walking conditions (over-ground and treadmill) in adults who indicate sleep disturbance on the PROMIS-29, as compared to those who do not indicate sleep disturbance.

H4d: Balance: Energy expenditure will be significantly greater at 125% of self-selected gait speed for treadmill walking in individuals with balance deficits, as indicated by decreased Functional Reach Test distance and decreased time until loss of balance during the modified Clinical Test of Sensory Integration in Balance conditions 3 and 4 (foam, eyes open and foam, eyes closed).

H4e: Functional Lower Extremity Strength: Energy expenditure will be significantly greater for self-selected and 125% of self-selected walking speed for both walking conditions (over-ground and treadmill) in adults with decreased functional lower extremity strength, defined as slower 5 Times

Repeated Chair Rise times.

H4f: Functional Mobility: Energy expenditure will be significantly greater at for walking at 125% of self-selected speed for both walking conditions (over-ground and treadmill) in adults with decreased functional mobility, defined as increased L-test time.

H4g: Agility: Energy expenditure will be significantly greater for walking at 125% of self-selected speed for treadmill walking in adults with agility deficits, defined as slower Four Square Step Test times and Figure-of-8 Walk Test times.

We expect that relationship may be stronger among adults with a unilateral below-the-knee amputation, but we are not powered to explore between-group differences. In fact, Aim 4 (and Aim 5) is (are) exploratory, and we are looking for trends in differences.

Specific Aim 5: Explore modifiable factors that may impact physical activity, as assessed with step activity monitors, including comorbidities, balance-confidence, fatigue, sleep disturbance, balance, functional lower extremity strength, functional mobility and agility among adults with (n=20) and without a unilateral below-the-knee amputation (n=20).

Hypotheses: For both adults with and without a below-the-knee amputation (after controlling for covariates):

H5a: Comorbidities: Average daily step counts will be significantly lower for adults with greater comorbidity burden, as assessed with the Cumulative Illness Rating Scale.

H5b: Balance-Confidence: Average daily step counts will be significantly lower for adults who have lower balance-confidence per the Activities-Specific Balance Confidence Scale.

H5c: Fatigue: Average daily step counts will be significantly lower for adults who indicate fatigue on the PROMIS-29, as compared to those who do not indicate fatigue.

H5d: Sleep Disturbance: Average daily step counts will be significantly lower in adults who indicate sleep disturbance on the PROMIS-29, as compared to those who do not indicate sleep disturbance.

H5e: Balance: Average daily step counts will be significantly lower in adults with decreased Functional Reach Test distance and adults who are unable to maintain balance for 30 seconds during m-CTSIB conditions 3 and 4 (foam, eyes open and foam, eyes closed).

H5f: Functional Lower Extremity Strength: Average daily step counts will be significantly lower in adults with decreased lower extremity functional strength, defined as slower 5 Times Repeated Chair Rise times.

H5g: Functional Mobility: Average daily step counts will be significantly lower in adults with decreased functional mobility, defined as increased L-test times.

H5h: Agility: Average daily step counts will be significantly lower in adults with worse agility as indicated by slower Four Square Step Test times and Figure-of-8 Walk test times.

Specific Aim 6: Explore the relationship between gait asymmetry, as quantified by spatio-temporal and 3D kinematic parameters (e.g. cadence, stance and swing time, step length, and joint position), and energy expenditure among inactive adults with a single, below-the-knee amputation (n=20) during treadmill walking at self-selected and fast walking speeds.

Hypothesis: Energy expenditure will be greater among inactive adults with a single, below-the knee amputation who demonstrate greater side-to-side differences in walking pattern during treadmill walking at both self-selected and fast walking speeds ($p<0.05$).

Specific Aim 7: Compare side-to-side differences in walking pattern (e.g. speed, step length, and joint position) between inactive adults with a single, below-the-knee amputation (n=20) and age-matched controls (n=20) during over-ground and treadmill walking using the APDM Mobility Lab software.

Hypothesis: For both over-ground and treadmill walking conditions, inactive adults with a single, below-the knee amputation will demonstrate greater side-to-side differences in walking pattern compared to age-matched controls ($p<0.05$).

Specific Aim 8: Explore the relationship between inspiratory muscle endurance, as quantified by an individual's sustained maximal inspiratory pressure (SMIP), and energy expenditure among inactive adults with a single, below-the-knee amputation (n=20) during treadmill walking at self-selected and fast walking speeds.

Hypothesis: Energy expenditure will be greater among inactive adults with a single, below-the knee amputation who demonstrate decreased SMIP values (p<0.05).

Specific Aim 9: Compare differences in inspiratory muscle endurance (measured by sustained maximal inspiratory pressure, or SMIP) between inactive adults with a single, below-the-knee amputation (n=20) and age-matched controls (n=20) using the PrO₂ device.

Hypothesis: Inactive adults with a single, below-the knee amputation will demonstrate decreased SMIP values compared to age-matched controls (p<0.05).

Specific Aim 10: Compare differences in inspiratory muscle endurance (measured by sustained maximal inspiratory pressure, or SMIP) between inactive adults with a single, below-the-knee amputation who have low back pain compared to those who do not report pain.

Hypothesis: Inactive adults with a single, below-the knee amputation who experience low back pain will demonstrate decreased SMIP values compared to individuals with a single, below-the-knee amputation who do not have pain (p<0.05).

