6. PROCEDURES

Describe all procedures involving human subjects for this protocol. Include copies of all surveys and research measures.

Overview: We propose to conduct a cross-sectional study of 22 adults with a unilateral transtibial amputation as compared to 20 sex-, age- (+/- 5 years), and body mass index- (+/- 5 kg/m²) matched controls. This one-time session is projected to take ~ 2hours on-site at the University of Delaware on the STAR campus within the Department of Physical Therapy.

Once contact is made with potential participants, inclusion and exclusion criteria will be examined in 2 phases, first over the telephone using a structured questionnaire, and then on-site by a research team member to validate inclusion and exclusion criteria obtained by telephone. Prior to telephone screening, verbal consent will be obtained from the participant. The on-site screening will occur after individuals have signed the informed consent.

All Participants will complete a series of questionnaires that will be sent via a mailing packet prior to the on-site evaluation. Questionnaires will take about 30 minutes to complete. Questionnaires included in this Mailing Packet will be the:

1. Demographics Mailing Sheet: Will provide pertinent demographic information necessary for characterizing and matching participants (i.e. age, sex).
2. Medical History Checklist: We would like to have participants complete this questionnaire as it will improve the efficiency and accuracy of the Cumulative Index Rating Scale.⁵⁰ Further, it will alert the physical therapist to any relevant problems that should be consider during physical performance testing and when testing energy expenditure during the 2 walking conditions.
3. Medication Sheet: Medication review using this sheet prior to physical performance testing and testing of energy expenditure during the 2 walking conditions will enhance patient safety and allow for appropriate interpretation of vital sign responses. This sheet will also allow increased efficiency and accurate scoring for the Cumulative Illness Rating Scale regarding comorbidities.⁵⁰
4. Activities Specific Balance Confidence Scale (ABC): The ABC is a valid³² 16-item

questionnaire where individuals rate how confident they are that they will not lose their balance or become unsteady with various ambulatory activities on a 0-100% scale, where 0=no confidence and 100%=complete confidence.²⁷

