Specific Aim 1: To determine reliability, intra-class correlation coefficients (ICCs) with 95% confidence intervals (CIs) will be calculated to evaluate test-retest reliability of physical activity

questionnaires. To evaluate validity between the self-report questionnaire data and activity-monitor obtained data that is continuous (e.g. steps/day, total activity in minutes/day), we will use ICCs with 95% CIs. We will quantify the relationship between the self-report data and activity-monitor data using Spearman's correlation coefficients. Interpretation will be as follows: $p \leq .25$ =weak correlation, $p=.26\text{--}.49$ =low correlation, $p=.50\text{--}.69$ =moderate correlation, $p \geq .70$ =high correlation.

Specific Aim 2: We will use receiver operating characteristic (ROC) curves to determine the minimal speed and cadence that corresponds to an oxygen consumption value of 10.5 mL/kg/min (i.e. 3.0 METs), as this has been identified by the World Health Organization as 'moderate intensity' activity.¹⁰

Specific Aims 3 and 6-10: We will use a MANOVA/MANCOVA to evaluate between-group differences with follow-up ANOVAs/ANCOVAs as appropriate ($p \leq 0.05$).

Specific Aims 4/5: Regression models will be used to explore relationships between energy expenditure (or average daily step counts) and each of the modifiable factors of interest, while controlling for relevant non-modifiable covariates, e.g. age, residual limb length.

Reported

Dissemination of results will occur through conference presentations and manuscript publications in peer-reviewed journals.

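### Aim 1 names over-reporting as the problem, but its validity analysis has no estimate of over-reporting and no rule that separates ranking from agreement

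*Combined protocol and SAP*

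**What the plan says.** Section 5 (Research Abstract) explains that monitors matter because "patients tend to over-estimate their level of physical activity", and describes the gap: "there has been little research looking at the accuracy of physical activity questionnaires in patients with lower-limb amputations". Aim 1 compares two questionnaires with monitor-derived walking time per day, bout duration and bouts per day. H1a sets an ICC of at least .75, for test-retest reliability only. H1b reads: "At least 1 self-report measure will demonstrate validity with ≥ 2 physical activity characteristics". It does not say what value of which statistic shows validity.

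In section 10 (Data), the Aim 1 text assigns validity for continuous monitor data, such as steps/day or total minutes/day, to ICCs with 95% CIs. The model, the single or average form, and the choice between consistency and absolute agreement are not given. It adds: "We will quantify the relationship between the self-report data and activity-monitor data using Spearman's correlation coefficients". The only interpretation scale is a set of correlation bands, the highest starting at .70. No mean difference, ratio or limits of agreement is planned anywhere in the document.

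**The concern.** The stated problem is one of level: patients report more activity than they do. Ranking patients correctly is a different property, and a questionnaire can have it while overstating everyone's minutes. If the analysis reports only association and an ICC whose definition is chosen later, the study will hold paired minutes from questionnaire and monitor and still not report the failing it set out to examine.

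H1b is also open-ended. With no threshold and no named deciding statistic, a good Spearman coefficient could carry a claim of validity that readers would take to include accuracy. Section 5 hopes to give healthcare providers a self-report measure for clinical practice, so the distinction matters to the intended user.

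**Working it through.** The document gives no precision or power figure for Aim 1, so there is nothing to reproduce. The check is how each planned statistic responds to known over-reporting.

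**Inputs.** From the document: n=20 for Aim 1 (section 6 recruits "22 adults with a unilateral transtibial amputation"); top correlation band from .70; ICC benchmark .75, stated for reliability only. Assumed, because the document gives no values: true walking time with mean 60 and SD 25 min/day; monitor noise SD 5; report noise SD *s* from 10 to 30.

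**Model.** Monitor = T + noise, with variance 625 + 25 = 650. Report = 2T + noise (doubling) or T + 60 + noise (additive). Both give a mean over-report *d* of 60 min/day, so d² = 3600.

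**Formulas (two-way, single measure).**
- Consistency ICC = 2·cov / (v₁ + v₂)
- Absolute-agreement ICC = 2·cov / (v₁ + v₂ + d²)

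**Doubling** (cov = 1250, v₂ = 2500 + s²):
- s=10: consistency 2500/3250 = 0.77; absolute 2500/6850 = 0.36
- s=30: consistency 2500/4050 = 0.62; absolute 2500/7650 = 0.33

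**Adding 60 min/day** (cov = 625, v₂ = 625 + s²):
- s=10: consistency 1250/1375 = 0.91; absolute 1250/4975 = 0.25
- s=30: consistency 1250/2175 = 0.57; absolute 1250/5775 = 0.22

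**Simulation at n=20** (4,000 studies per setting), medians for s=10 to s=30:

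| Over-report | Spearman | Consistency ICC | Absolute-agreement ICC |
|---|---|---|---|
| Doubling | 0.95 to 0.82 | 0.77 to 0.62 | 0.36 to 0.32 |
| +60 min/day | 0.89 to 0.60 | 0.91 to 0.57 | 0.24 to 0.21 |

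The simulated ICCs match the formulas to within about 0.01. In the low-noise case the same data give an ICC of 0.91 or 0.24, depending on a choice the plan leaves open.

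**Limiting case, exact doubling without noise.** Spearman is 1.00 and the consistency ICC is 4/5 = 0.80 whatever the spread. The absolute-agreement ICC is 4·CV²/(5·CV² + 1), which runs from 0.25 at a between-person CV of 0.3 to 0.67 at 1.0 (CV range assumed).

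**What a bias estimate would deliver.** The 95% CI half-width for the mean difference is t(0.975, 19)·SD/√20 with t = 2.093. An SD of differences of 15, 20 or 30 min/day gives ±7.0, ±9.4 or ±14.0. The scenarios above imply SDs from √(25 + 100) = 11.2 (additive, s=10) to √(625 + 25 + 900) = 39.4 (doubling, s=30), that is ±5.2 to ±18.4. All are small against a 60-minute over-report.

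**The case against.** The strongest reply is that section 10 assigns validity to the ICC and uses Spearman only to describe association. If the ICC is the absolute-agreement form, over-reporting is already penalised, as the values of 0.21 to 0.36 show. That stands: it would be wrong to infer that no planned statistic could react to over-reporting. But the form is not stated, H1b does not say the ICC decides, and even that form mixes bias with scatter and between-person spread.

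Three stronger readings are tempting and not supported.
- *Nearly every such study would call the questionnaire valid.* The share with Spearman at or above .70 under +60 min/day is about 98 to 99% at report noise SD 10, but about 64% at SD 20 and 25% at SD 30. Under doubling it falls only to about 87% at SD 30. In any case, the plan does not define the top band as validity.
- *Inactive patients would be classed as meeting 150 minutes per week.* Section 5 states that target for moderate-intensity activity in bouts of at least 10 minutes. No planned analysis classifies patients against it.
- *Any non-zero mean difference is over-reporting.* Section 6 says the IPAQ covers work, transport, household and gardening, and leisure, while the ankle monitor records steps and is worn with the prosthesis. Part of a difference in total activity may be activity the monitor does not record.

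**Conclusion.** The concern holds as a gap between the stated problem and the planned analysis. The plan has no estimate of the size or direction of over-reporting, leaves open an ICC choice that can change the answer greatly, and has no H1b criterion to prevent a validity claim based on ranking alone.

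That Spearman is blind to uniform over-reporting, and that a consistency ICC is blind to a constant offset, holds without any assumption. The numerical sizes rest on assumed means, SDs and noise. As report noise rises, Spearman and the consistency ICC fall too, so the contrast with absolute agreement is widest when patients over-report consistently. The finding does not show that either questionnaire is biased in this population, or that the investigators would in fact claim validity from Spearman alone.

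**What to change.** In the Aim 1 text of section 10:

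1. For questionnaire and monitor values in the same unit (minutes/day), name the two-way, single-measure, absolute-agreement ICC.
2. Pair the monitor week with the questionnaire re-completed at its end, so that both cover the same 7 days.
3. Report the mean paired difference, or the ratio on the log scale, with 95% CI and Bland-Altman limits of agreement.
4. Where possible, compare the questionnaire's walking items with monitor walking time. State that a difference in total activity may partly reflect non-stepping activity.
5. In H1b, describe any conclusion that rests on Spearman as validity for ranking only, with the bias estimate beside it.

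Do not make H1b turn on whether the CI for the mean difference excludes zero. Such a rule has no acceptable margin, so it could fail a precise, trivial bias and pass a large, imprecise one.

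The cost is a few sentences and no new data. A questionnaire may earn a more qualified validity claim, and at n=20 the bias would be known only to about ±7 to ±14 min/day if the SD of differences is 15 to 30.

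### H4b, H4c, H5c and H5d word PROMIS-29 fatigue and sleep disturbance as undefined yes/no groups although graded scores are collected, and H4d and H5e define the same m-CTSIB predictor differently

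*Combined protocol and SAP*

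**What the plan says.** All of this is in the combined protocol and SAP.

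- **Fatigue.** Section 5, H4b, sets "adults who indicate fatigue on the PROMIS-29, as compared to those who do not indicate fatigue". For steps, H5c reads "Average daily step counts will be significantly lower for adults who indicate fatigue on the PROMIS-29" and names the same comparison group.
- **Sleep disturbance.** H4c sets "adults who indicate sleep disturbance on the PROMIS-29, as compared to those who do not indicate sleep disturbance". H5d reads "Average daily step counts will be significantly lower in adults who indicate sleep disturbance on the PROMIS-29", again against those who do not.
- **Balance, energy expenditure.** H4d uses "decreased time until loss of balance during the modified Clinical Test of Sensory Integration in Balance conditions 3 and 4", with no threshold.
- **Balance, step counts.** H5e refers to "adults who are unable to maintain balance for 30 seconds during m-CTSIB conditions 3 and 4". The other half of H5e stays graded: "Average daily step counts will be significantly lower in adults with decreased Functional Reach Test distance".
- **Neighbouring factors.** Comorbidity burden, balance confidence, chair-rise time, L-test time and the agility tests are all worded as more or less of a measured quantity.
- **The instrument.** Section 6 (mailing packet, PROMIS-29) lists fatigue and sleep disturbance among the domains and describes subscales on which populations score higher or lower.
- **The analysis.** Section 10, Aims 4/5, says regression will relate the outcome to each factor, adjusted for non-modifiable covariates such as age and residual limb length. It does not say whether a factor enters as a score or as yes/no.
- **Status.** Section 5 declares Aims 4 and 5 exploratory.

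**The concern.** Two things are at stake for the PROMIS-29 factors. First, splitting a graded score into two groups throws away the differences within each group, and the cost is felt most in a small sample: 20 adults with and 20 without an amputation. Second, nothing in the plan says what score counts as indicating fatigue or sleep disturbance, so the threshold could be set after the outcome data are in hand. For H4b and H4c that single choice runs through three speeds and two walking conditions, that is 3 × 2 = 6 contrasts for each factor.

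The m-CTSIB issue is one of consistency. The same two test conditions enter the energy aim as a time and the step-count aim as pass/fail, and no reason is given.

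**Working it through.** The documents give no power, effect size, cut-off or prevalence for Aims 4 and 5, so there is no planned figure to reproduce. What follows is conditional on the hypotheses being analysed as worded.

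**Inputs from the documents.** n = 20 + 20 = 40 (Section 5, Aims 4 and 5). Sections 6 and 7 recruit 22 + 20 = 42; this is checked below.

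**Assumptions.** Roughly normal PROMIS-29 score; linear relation with the outcome; two-sided 5% level (Section 10 states 0.05 for Aims 3 and 6-10 but gives no level for Aims 4/5); true correlation r = 0.40; splits from 50/50 to 90/10.

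**Step 1: information kept by a split.** With a share p above the cut, c the corresponding normal quantile and φ the normal density, the efficiency relative to the graded score is E = φ(c)² / [p(1−p)].

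- 50/50: 0.3989² / 0.25 = 0.637
- 70/30: 0.3477² / 0.21 = 0.576
- 80/20: 0.2800² / 0.16 = 0.490
- 90/10: 0.1755² / 0.09 = 0.342

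The loss is 1 − E and the effective sample is 40 × E. The correlation shrinks to r√E.

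**Step 2: power by Fisher's z.** Power = Φ[atanh(r√E) × √(n−3) − 1.960].

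- Graded, n = 40: atanh(0.40) = 0.4236; × √37 = 2.577; − 1.960 = 0.617; power 0.731.
- 50/50: r√E = 0.40 × 0.798 = 0.319; 0.3307 × √37 = 2.012; − 1.960 = 0.052; power 0.521.
- 80/20: r√E = 0.40 × 0.700 = 0.280; 0.2877 × √37 = 1.750; − 1.960 = −0.210; power 0.417.

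| Coding | Information lost | Effective n of 40 | Power, n = 40 | Power, n = 20 |
|---|---|---|---|---|
| Graded score | 0 | 40 | 0.731 | 0.416 |
| 50/50 split | 36% | 25.5 | 0.521 | 0.275 |
| 70/30 split | 42% | 23.0 | 0.479 | 0.252 |
| 80/20 split | 51% | 19.6 | 0.417 | 0.219 |
| 90/10 split | 66% | 13.7 | 0.305 | 0.164 |

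The n = 20 column applies if models are fitted within one group, which the residual limb length covariate suggests for the amputation group.

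**Step 3: sensitivity.**

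- Two covariates (n − 3 − 2 in place of n − 3), n = 40: 0.708 graded, 0.499 at 50/50, 0.398 at 80/20.
- n = 42, no covariates: 0.754, 0.542 and 0.435.
- Simulation check at r = 0.43, n = 40, 20,000 runs: about 81% graded, then 60%, 56%, 48% and 34% for the four splits. The formula gives 80%, then 59%, 54%, 47% and 35%.

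The gap between graded and split coding barely moves.

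**Step 4: m-CTSIB.** Here the check is textual. H4d and H5e name the same conditions (foam, eyes open and eyes closed). One uses time to loss of balance, the other failure to reach 30 seconds.

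**The case against.** The strongest objection is that Section 10 does not commit to yes/no coding. It names regression, which takes a score as readily as an indicator, so a reader who infers that the graded data will certainly be discarded goes further than the documents do. That stands. The finding is that the only text describing these predictors is dichotomous, with coding and cut-off left open, and the loss follows only if that text is followed.

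A reader might also infer that balance as a whole is reduced to yes/no in H5e, at a similar loss. The documents do not support that. Functional Reach is graded in the same hypothesis. For the m-CTSIB, the 30-second criterion suggests that times stop there, although Section 6 gives no timing details. If they do, many participants may share the top value and the normal-score calculation does not apply. Under an assumed 30-second cap, the loss is about 46-53% if the outcome is linear in the capped time. If the outcome follows the underlying ability, the loss is about 13% when half fail, and the pass/fail version does slightly better when 30% or fewer fail. No efficiency figure can be claimed for this part. Nor does any aim propose comparing the m-CTSIB result for energy with that for steps, so the mismatch calls for consistency and spoils no planned comparison.

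It is also fair that the splits and r = 0.40 are assumptions, and that a cut-off justified in advance would by itself remove the scope for a post-hoc choice. It would not recover the lost information.

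Finally, Aims 4 and 5 are exploratory. That lowers the weight of the point but is no reason to prefer the weaker coding, since a real trend becomes easier to miss and a late-chosen threshold makes a spurious one easier to find.

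**Conclusion.** The point holds for the PROMIS-29 factors, conditionally. Four hypotheses state a two-group contrast with no cut-off, on an instrument that yields scores. Followed as worded, with a roughly normal score and a linear relation, the split costs about 36% of the information at best and 51% to 66% at 80/20 to 90/10. At r = 0.40 and n = 40 that means power of 52% or 42% (50/50 or 80/20) where the graded score gives 73%. Which split would apply cannot be known, because the documents give no prevalence.

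The m-CTSIB point holds only as an unexplained difference between H4d and H5e, with no size attached.

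Severity is modest: no confirmatory conclusion rests on these aims, but the improvement uses data already being collected.

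**What to change.** 1. Reword H4b, H4c, H5c and H5d so that higher PROMIS-29 fatigue or sleep-disturbance scores are predicted to go with higher energy expenditure or lower step counts.
2. State in the Aims 4/5 text of Section 10 that these two scores enter the regressions as continuous predictors.
3. If a yes/no comparison is still wanted, label it secondary and fix and justify its cut-off before the outcome data are examined.
4. Use one m-CTSIB definition in H4d and H5e, and state how times at the ceiling will be handled.

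Items 1 to 3 change wording only: same data, same participants, same regression models. Item 4 also needs a short methodological decision about the ceiling, but no new measurement.
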